In addition to health services utilization costs associated with Usual Primary Care (UPC) for chronic pain, intervention costs in this arm will be minimal but will include training of UPC veteran participants and primary care staff on use of the Whole Health Resource Directory. For the WHT and PC-GE interventions, intervention costs will be calculated using a combination of VA administrative and clinical staff time devoted to each of the active interventions as well as costs associated with participant services utilization. Specifically, for the WHT intervention, visit costs will include team conferencing time and clinician time, including coach time (hourly rate for each team member) that will be ascertained using clinic visit notes in the electronic medical record (EMR) plus estimated administrative time for each clinical visit. PC-GE intervention costs will be estimated by accounting for the number of PC-GE modules for patient participants per site and the clinician and administrative time associated with each module. All other VA and non-VA community care healthcare costs will be collected using Decision Support Systems (DSS) National Data Extracts, the official cost managerial accounting system for VHA as well as new databases for computing costs for non-VA community care (after the Mission Act). These analyses will focus on VA and non-VA outpatient visits and outpatient pharmacy costs. Outpatient costs for the main analysis will be organized in the following groups by stop code field: integrative (CIH), primary care, emergency department, mental health, substance use disorder care, specialty pain care, ancillary, physical health specialty, and other. Outpatient VA medication costs will also be assessed using VA DSS data and will be divided by medication

class into opioid, non-opioid pain related, and other. We will also track inpatient admissions of all study participants during follow-up.

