  - National Opioid Dashboard: Detailed information about opioid prescribing for chronic pain, opioid safety information, e.g., urine drug tests, dispensing of naloxone kits, opioid informed consent, plus common adverse events associated with opioids—suicide, overdose, accidents and injuries.
  - Managerial Cost Accounting (MCA) (Decision Support System, DSS) National Data Extracts and the Health Economics Resource center (HERC) Average Cost Datasets (for the planned Budget Impact Analysis, see below).
  - COVID-19 Shared Data Resource.

Because some CIH care (e.g. acupuncture and chiropractic care) is by referral to community care providers through the Mission Act, we will also obtain the relevant VA administrative databases that capture care delivered by community providers (Purchased Care, Payment Integrity Tool (PIT) and the Fee Basis Claim System). Of note, because this is an evolving area for VHA, new databases are being added to capture care purchased in the community and we request permission to use these newer databases as they come online.

**3. Description of Patient-Reported Measures:** Patient-reported outcome measures will be collected at baseline, 3, 6, 9, and 12 months. All outcome assessments will be conducted as telephone interviews by research staff masked to treatment arm assignment. *Full-length* outcome assessments will be conducted at baseline, 6, and 12 months. *Abbreviated* assessments will be conducted at 3 and 9 months. Participant responses will be recorded by study staff entering responses directly into REDCap, data collection and management software

approved by VA. A participant stipend (\$50 for each of the full-length assessments and \$25 for the brief assessments) will be provided. We have used outcome assessment protocols of similar or greater duration in multiple trials involving patients with mental health conditions, pain and opioid use and have found them to be well-tolerated and associated with minimal missing data and attrition. If assessment burden becomes a problem at any point during the study, participants will be given the option of completing a minimum assessment composed of core outcome measures. We will use standard validated instruments to ascertain our primary and secondary outcomes.

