## Missing Data

First, we will assess the amount of missing data and its impact on the statistical power. Second, we will examine the patterns of missing data and specify plans for various sensitivity analyses based on different assumptions of the missing data mechanisms.

Our sample size, 765, was computed based on an assumption of 20% loss-to-follow-up. This means that if we have 612 subjects with outcomes data, we will have sufficient power (90%) to detect pre-specified effect sizes (which vary by different pair-wise comparisons). We place emphasis on preventing and minimizing missing data in study design and execution. One of the strategies is to continue collecting outcomes data even if a participant withdraws or deviates from the assigned treatment. As long as the patient has not withdrawn consent, we will continue to collect outcomes data from surveys and VA administrative data sources (which supplement data other than the primary outcome). We anticipate that this strategy will help minimize missing outcomes data and preserve statistical power.

Before conducting the analyses, we will examine the patterns of missing data with a focus on intervention arms, enrollment sites, time periods, and potential prognostic factors such as severity of comorbidities and post-randomization time-dependent variables. This examination will help us make assumptions about missing data mechanisms.

In the main analysis, we consider it plausible to hold the “missing at random” (MAR) assumption. With this assumption, there is no systematic difference between subjects who are and are not lost to follow-up, and the probability of missingness only depends on observed data. This is supported by our effort to collect a range of information that could explain the missingness. Under this assumption, our planned analytical strategies are unbiased. These will include a mixed-effects linear regression, inverse probability weighting and multiple imputation (MI).

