## 9.0 Safety Assessments

## 9.1 Specification of Safety Parameters

- Endorsement of mental health-related issues (e.g., suicidal ideation) during telephone assessments, visits with PCP, or intervention related visits
- Regular assessment of pain and functioning during the telephone sessions

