## 9.4 Reporting Procedures

Site PIs will be notified by the site project coordinator(s) immediately of any possible event that poses a risk to a subject. In addition, at least one of the PIs ([name] or [name]) or both will also be notified. The PI(s) will promptly respond to the problem and mitigate any negative consequences for the participant(s) involved. The PI and/or study coordinator will report the event to the IRB of Record within the timeline as follows:

a. **Unanticipated Problems Involving Risks to Subjects or Others.** Members of the VA research community are required to ensure that unanticipated problems involving risks to subjects or others in research are reported promptly to the IRB within five business days.

b. **Serious Unanticipated Problems Involving Risks to Subjects or Others.** Within five business days of becoming aware of any serious unanticipated problem involving risks to subjects or others in VA research, members of the VA research community are required to ensure that the problem has been reported in writing to the IRB.

c. **Local Unanticipated SAEs.** Within five business days of becoming aware of any local (i.e., occurring in the reporting individual's own facility) unanticipated SAE in VA research, members of the VA research community are required to ensure that the SAE has been reported in writing to the IRB.

If an AE/SAE is reported by a veteran directly to the local study coordinator at their participating site, the local study coordinator will complete an AE form on the study database within 24 hours of notification. If this event also meets the criteria for an SAE, the local study coordinator will indicate this on the AE form in the study database within 24 hours. For SAEs, the local study coordinator will download a pdf of the completed SAE form and send this as an attachment via encrypted email (see draft email A below) to the Project Manager, LSI, and Co-Principal Investigators Drs. [name] and [name]. The LSI and PIs will confer via email to determine the severity and relatedness of the event to the study intervention within 48 hours of notification. The Coordinating Center will follow VA Central IRB reporting guidelines as appropriate.

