If an AE/SAE is reported by a veteran during a telephone research assessment to a masked coordinator located at another site, the masked coordinator will immediately send an encrypted email (see draft email B below) to the local study coordinator to notify them of the event. The local study coordinator at the veteran's participating site will call the veteran participant to learn details of the event and complete the AE form on the study database, within 24-48 hours of event notification. If this event also meets the criteria for an SAE, regardless of whether related to the study or not, the local study coordinator will indicate this on the AE form in the study database within 24 hours. For SAEs, the local study coordinator will download a pdf of the completed SAE form and send this as an attachment via encrypted email (see draft email A below) to the Project Manager, LSI, and Principal Investigators Drs. [name] and [name]. The LSI and Co-PIs will confer via email to determine the severity and relatedness of the event to the study intervention within 48 hours of notification. The Coordinating Center will follow VA Central IRB reporting guidelines as appropriate.

The PIs have developed a suicide and homicide ideation safety protocol for other studies with Veterans that will also be used for this study in the event of active suicidal or homicidal ideation.

If we are unsure whether a document requires submission or reporting, we will contact the VA Central IRB @ the toll-free number [contact] or [[contact]](mailto:[contact]).

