7.4 Exploratory Analyses/ Per Protocol Analyses

Responder analysis (exploratory analysis). Response will be defined as at least a 30% improvement in BPI interference score from baseline. Reduction in pain/interference of this size has been found to be clinically meaningful and IMMPACT recommended that the percentage of participants with this reduction be reported in chronic pain clinical trials.¹⁶ In addition, they recommended the percentages of patients with at least 50% improvement (substantial improvement) also be reported. We will also report the number who achieved a reduction in pain interference of at least 1 point (minimal clinically important difference for BPI interference).

With the COVID-19 pandemic, treatment implementation may have varied during the study period, and there may have been incomplete adherence to the interventions and outcome assessments. We collected additional time-dependent data to attempt to capture these fluctuations (variables such as mode of treatment delivery, availability of pain management services, and COVID infection status). Our strategies are to: (1) adjust for time-dependent variables that reflect changes in the implementation of treatments, and (2) perform analyses using interactions to see whether the treatment effect differs by time periods, sites, and site characteristics such as degree of availability of pain management services. Inherently these will have limited power, and no further adjustments will be made for multiple testing given the exploratory nature of these analyses.

Additional analyses will consider a per protocol population and repeat the primary analysis in this population. In the per protocol population, we will include any subject who minimally or completely adhered to treatment assignment indicated by the protocol, but will exclude the protocol violators who did not meet the following minimal threshold criteria: if randomized to the WHT arm, participants attended at least 6/8 coaching sessions, the WHT initial visit, and at least 2 of 3 follow-up WHT visits; if randomized to the PC-GE arm, participants attended the orientation and at least 4 of 5 core modules. In addition, participants will be excluded from the per-protocol analysis if they received prohibited concomitant interventions or if they missed all outcome measurements.

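### No way of finding SAEs is specified beyond the veteran's own report, so deaths and admissions among non-responders may go unrecorded, perhaps unevenly by arm, although VA data on them are already planned

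*Protocol*

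**What the plan says.** **How an event reaches a form.** Protocol 9.4 gives two worked routes. The first opens "If an AE/SAE is reported by a veteran directly to the local study coordinator at their participating site". The second opens "If an AE/SAE is reported by a veteran during a telephone research assessment", after which the masked assessor alerts the local coordinator, who telephones the veteran for details and completes the form. The schedule in Protocol 7.1 places AE collection at the 3-, 6-, 9- and 12-month calls. For a missed timepoint, Protocol 6.4 provides for repeat calls and voicemails, and mentions no check of the records for events.

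**What counts as serious.** Protocol 9.3 and SAP 5.4 both include death and inpatient hospitalisation.

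**What the trial collects from records anyway.** Protocol 4.2 states: "We will also track inpatient admissions of all study participants during follow-up". Protocol 7.2.4 adds the dates on which veterans leave VA care (some through death), inpatient and emergency use, and community care that the VA pays for. It also adds an opioid dashboard covering "common adverse events associated with opioids—suicide, overdose, accidents and injuries". The Missing Data part of Protocol 8.6 keeps administrative collection going after a participant leaves the assigned treatment, unless consent is withdrawn.

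**What the safety analysis uses.** SAP 9.5 tabulates SAEs, AEs and unanticipated problems as defined in SAP 5.4. It speaks of two groups, although the trial has three arms. It does not mention the administrative data.

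**The concern.** A participant who has died cannot make a report, and one who is in hospital or no longer answering may not. If the form depends on a report, the events in the SAE definition are the ones most exposed to being missed. The trial could then publish an SAE table that disagrees with its own admissions data.

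The second risk is to the comparison between arms. Protocol 6.1 and 7.2.4 have local coordinators telephone WHT and PC-GE participants around each visit or session to collect PEG and PHQ-4. UPC participants have no equivalent study contact. Those calls are not described as AE interviews, but each one gives the veteran a chance to report an event to the coordinator. Fewer recorded events in UPC could therefore reflect fewer conversations.

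**Working it through.** **Step 1. Is any other detection source named?** Four places could supply one:
- The opening of Protocol 9.4 has coordinators alert the site PI to any event that may put a participant at risk. It does not limit the source, and it does not name one.
- SAP 5.4 starts documentation when an AE or SAE occurs. It does not say how the coordinator learns of it.
- Protocol 9.2 has study clinicians pass concerning findings to the participant's other treating clinicians. It does not route them to an AE or SAE form.
- Protocol 4.2 and 7.2.4 obtain admissions, deaths and opioid-related events for costs, utilisation and outcomes. Neither feeds them to the form.

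The first two say what follows once an event is known. None says how an unreported event is found.

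**Step 2. Contact by arm.** All arms have four follow-up assessment calls. PC-GE adds an orientation, five core sessions and a discharge session, 1 + 5 + 1 = 7 in all, each with a coordinator call. WHT adds an initial visit and at least three further team visits, so at least 4, each with a coordinator call, plus coaching sessions. UPC adds none.

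**Step 3. Reproduce the plan's figure.** Protocol 8.6 says "Our sample size, 765, was computed based on an assumption of 20% loss-to-follow-up" and refers to power being sufficient "if we have 612 subjects with outcomes data".
- 765 × (1 − 0.20) = 612, as stated.
- 765 × 0.20 = 153 without outcome data; by planned arm size, 341 × 0.20 ≈ 68 in each of WHT and PC-GE, and 83 × 0.20 ≈ 17 in UPC.
- For the 769 that the SAP gives as enrolled, 769 × 0.20 ≈ 154.

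**Step 4. Illustrate the size.** The documents give no SAE rate and do not say how much follow-up is unobserved in those lost. Both are assumptions here: r is the 12-month risk of at least one SAE, and u is the share of these participants' follow-up that yields no report.

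Participants with an unreported SAE ≈ 153 × r × u

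| r | u = 25% | u = 50% | u = 100% | Expected in all 765 (765 × r) |
|---|---|---|---|---|
| 2% | 0.8 | 1.5 | 3.1 | 15.3 |
| 5% | 1.9 | 3.8 | 7.7 | 38.2 |
| 10% | 3.8 | 7.7 | 15.3 | 76.5 |
| 20% | 7.7 | 15.3 | 30.6 | 153.0 |

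The range is about 1 to 31. If risk is equal in those lost and those retained, the share of participants with an SAE who go unreported is 0.20 × u, or 5% to 20% whatever the value of r. It is larger if risk is higher in those lost, but the documents do not show that it is.

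**The case against.** **The two paragraphs in 9.4 may be workflow for particular cases, not an exclusive list.** This is fair. The opening of 9.4 and SAP 5.4 are not restricted to veteran reports, Protocol 9.1 mentions endorsements at PCP and intervention visits, and staff may hear of a death informally. A reader might infer that an SAE is recorded only if the veteran reports it; the documents do not go that far. What stands is that no other source is specified or assigned to anyone.

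**The 20% is loss of outcome data, not of all contact.** Also fair. A reader might infer that 153 people go unobserved for a full year. Events before loss, or raised at other calls, can still be reported, so the u = 100% column is a ceiling.

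**The named safety parameters are analysed.** Protocol 9.1 lists mental-health endorsement and "Regular assessment of pain and functioning during the telephone sessions", and a reader might infer that these are never examined because SAP 9.5 omits them. That is wrong. Pain interference is the primary outcome; pain intensity, functioning and suicidality are secondary outcomes; and SAP 5.4 counts passive suicidal ideation as an AE, so it is tabulated. What is missing is a safety display: SAP 7.4 counts improvement only ("Response will be defined as at least a 30% improvement in BPI interference score from baseline", plus the 50% and 1-point counts). Turning the 30% cut-off round to define worsening would not be using an SAP threshold, because the SAP sets it for improvement alone.

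**The records are incomplete.** True. Community care appears only if the VA pays for it. Only the admissions sentence says that it covers all participants; for the dashboard this is not stated.

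**The DSMB may see more than these texts show.** The SAP contents list an appendix of DSMB tables whose text is not available here, so no claim is made about what the DSMB has seen.

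**Conclusion.** The point holds as a gap in specification with a plausible effect on the safety results. Followed as written, the plan can leave out deaths and admissions among participants who stop responding, and can ascertain events less fully in UPC than in the active arms. Records that would show many of these events are already to be obtained, but are not linked to the safety analysis.

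The size is roughly 1 to 31 participants with an unreported SAE. This rests on the plan's 20% loss, an assumed 12-month SAE risk of 2% to 20%, and an assumed 25% to 100% of follow-up unobserved in those lost. The direction of any bias between arms can be argued from the contact schedule, but its size cannot be estimated from the documents. The change should be made before final lock; it does not affect the primary efficacy analysis.

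**What to change.** **SAP 9.5.** Tabulate deaths, inpatient admissions and overdose or suicide events from the planned VA extract for all randomised participants, by the three arms, over the same 12 months from randomisation. Replace the reference to two groups. State that coverage is limited to VA and VA-paid care.

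**Reconciliation.** Compare the extract with the SAE forms at final lock, and before any remaining DSMB report for which an extract is available. Open a form for any event not already recorded. With 769 already enrolled, the comparison at lock is the essential step. The SAP allows changes until final data lock and before unblinding. Protocol 9.4 should name the records as a detection source so that the two documents agree.

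**Optional descriptive display.** By arm and visit, show the proportion whose BPI interference is at least 1 point worse than baseline (1 point being the size SAP 7.4 treats as minimally important for improvement), and new suicidal ideation on the PHQ-9 among those without it at baseline. This adds a safety view of outcomes already analysed for efficacy.

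**Cost.** Programming on data already planned, with no new participant contact. More SAE forms will need severity and relatedness review by the site investigator and PIs, and the recorded SAE rates will look less favourable.

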## 9.5 Follow-up for Adverse Events

If a patient is deemed passively suicidal during the course of the study, appropriate referrals to mental health services will be made. If a patient becomes actively suicidal after enrollment in the study, the study team will activate the study's suicide protocol (see Appendix 5.0. Suicide Protocol), which includes notifying the site PI or designated study clinician of the situation so that they can assess the patient and obtain the proper assistance, if needed. Thus, if the site PI or designated clinician is sick or on vacation, they will need to designate a covering clinician to handle such emergencies. Once the urgent situation is addressed, the site PI or other member of the study team will notify the participant's PCP either over the phone, encrypted email or through a CPRS clinic note.

## **9.6 Data and Safety Monitoring Board (DSMB)**

The DSMB will act in an advisory capacity to NCCIH to monitor patient safety for wHOPE. [name] of the University of Washington has been selected by the NCCIH to serve as the DSMB Chair. [name] will serve as the NCCIH DSMB Executive Secretary (ES). The DSMB will meet annually at the call of the Chair, with advance approval of the DSMB ES. On a scheduled basis (as agreed upon by the DSMB), an Interim Study Report will be developed by the Data Coordinating Center; and will be developed every 4 months following a scheduled DSMB meeting, or at another time as required by the DSMB. The DSMB Roster for wHOPE is as follows:

## **10.0 Data Collection and Quality Assurance**

### **10.1 Data Collection**

Data collected from the baseline and follow-up assessments will be entered electronically into REDCap, a secure SFVAMC approved web-based tool for building surveys. Additionally, AEs/SAEs will be collected through REDCap. A secure SQL database will also be used to track recruitment and enrollment. The SQL database will also be used to store VA administrative data for study outcomes. This will also include any data collected at the Point of Care as health factors.

